#### 2.1 Research question

The aim of this initial randomised, controlled, prospective feasibility study is to determine the acceptability and efficacy of the step-it pedal as an adjuvant therapy for leg lymphoedema with a primary clinical outcome measure of leg volume. This is a pilot aiming to assess the feasibility of conducting a full randomised clinical trial in the future.

#### 3. INVESTIGATIONAL DEVICE + INTERVENTION

The Step-It pedal is developed at Uppsala University Hospital through collaboration between [name] and vascular surgeon [name]. The StepIt rocker pedal is designed to mimic the walking movement and make the foot bend and stretch. This design is aimed to stimulate the calf muscles and increases circulation in the legs, thereby decreasing the risk for blood clotting and circulation problems. The step-it pedal is 95mm by 230mm by 40mm, weights 212 gram and is made out of ABS-plastic with a silicon footpad (figure 1).

Resistance of the pedal is circa 6 kg and cannot be adjusted. There is no recommended tempo indicated for the pedal, simply because some patients will be more able to do the movements. The videos on the Step-It website show a frequency of roughly 1 second downwards, 1 second upwards motion (https://www.youtube.com/watch?v=nsAZm5TxEIY&feature=youtu.be and http://www.stepit.com/ ). However, in the leg lymphoedema target population , patients will be encouraged to work at a minimum of 2 second downwards, 2 second upwards motion frequency.

The StepIt pedal is to be used:

Two short sessions per day, and for each session: total of 5 minutes for each leg (easiest to perform 1 minute per leg, then changeover, to allow rest of each leg in between exercise), making it 10 minutes of exercise per session. Total per day will be 10 minutes per leg.

A standard pedometer will be clipped onto the front of the pedal to allow measurement of pedal movement activity.

Figure 1. Step-it pedal

#### 4. STUDY HYPOTHESIS

#### 4.1 **Primary objective**

• To assess the feasibility of conducting a full RCT in the future

#### 4.2 Secondary objective

• To assess the acceptability and efficacy of the Step-It pedal as an adjuvant therapy for lymphoedema symptom control.

#### 5. STUDY PROTOCOL

#### 5.1 Study design and timeline

This concerns a multi-centre, controlled prospective randomized study. The study will be carried out at GP practices and the Hospice at Home (Carlisle and Lakeland) lymphoedema service clinics, and the study is sponsored by Cumbria by North Cumbria Integrated Care NHS Foundation Trust. The study will take place in local community setting with support and oversight from Clinical Lymphoedema Specialists and research staff.

Month	Setup	Recruitment	Analysis	Finalise
Oct-19	Submission for			
	HRA approval			
Nov-19	NIHR portfolio			
	adoption			

#### Table 2. Anticipated timeline

Dec-19	HRA and Trust approval	Start recruitment		
Jan-20		Start recruitment		
Dec-22		Finish recruitment		
Mar-23			Analyze data	
May-23				Finalise analysis
				& report

#### 5.2 **Participant identification & consent**

Patients with leg lymphoedema will be screened for eligibility for this study by the Chief Investigator. All eligible patients will be invited to take part until the required numbers have been achieved. Patients will be recruited sequentially and randomised into two groups: one control group receiving care as usual and one intervention group receiving care with the StepIt device. The eligible patient population is defined in the Inclusion and Exclusion criteria section. A delegated member of the research team will join the (non-research) lymphoedema care specialist to the first appointment provided the patient has consented to this verbally. During this visit /clinic appointment the study will be discussed in further detail and the participant has the opportunity to ask questions that they may have. If potential participants meet the eligibility criteria, the patients can be consented by the Clinical Lymphoedema Specialists or Research Nurses/Practitioners , the latter as long as the patient's verbal consent has been sought from the treating clinical staff. A screening form will be completed for potentially eligible patients to confirm that they indeed meet the trial criteria.

During the screening visit all patients get the opportunity to try out the Step-It pedal. This also functions as a screening tool, since those patients who cannot perform the required ankle/foot movements cannot enter the trial. Significant discomfort will also be a reason for exclusion. The outcomes of this screening exercise will be recorded in the screening log.

Patients will be given > 24 hrs to consider if they wish to take part, and can ask questions regarding the study. If they understand the nature of the study and are happy to take part, written informed consent will be obtained.

Participants will receive no incentives and consent will be regarded as a process and not a one off event. Participants are free to withdraw from the study at any time without the need to give any reasons for withdrawal. Their standard care will not be affected by either declining to participate in the study or withdrawing during participation.

#### 5.3 Recruitment

Participants will be randomised to either the control group (standard care) or the intervention group (standard care plus use of a StepIt pedal) for 12 weeks. Patients in both groups will be given the usual lymphoedema management information, but those in the intervention group will be issued with a StepIt Pedal to use daily for foot and ankle exercises. The participants will be asked to report on their activity at the end of trial (self-reported compliance Likert scale question). At their discharge visits participants are also asked to provide their wider opinion on trial participation. All participants will have demographic data obtained and the following base line measures (Table 3):

T	able	3.	Baseline	measures
•	abic	٠.	Duschine	measures

Weeks	0	6#	12#
Leg volume	Х	Х	Х
Ankle circumference	Х	Х	Х
Ankle range of motion	Х		Х
Visual analogue pain score	Х	Х	Х
LYMQOL-Leg	Х	Х	Х
EQ-5D-5L	Х	Х	Х
PEDAL experience questionnaire			Х

# Allowed to be up to 2 weeks early or late

During the recruitment process the research team acts as a contact point and coordinator for patients requiring information and support. If concerns are raised on participants (mental) wellbeing based on the home visits or outcome of the assessments, referral of patients/families on to other professional agencies will be done as appropriate and according to the Trust guideline.

#### 5.4 Follow-up

Patients are in the study until they are discharged from the lymphoedema service, GP practice, or for the maximum period of 12 weeks; we anticipate most, if not all, patients not to be discharged during their trial participation period. The patient will be followed up as they would in normal clinical practice. The Clinical Lymphoedema Specialist will manage the leg lymphoedema as per routine care, and will conduct the measurement of the leg volume. In clinic, the Clinical Lymphoedema Specialist or Researcher will randomise the patient, hand out the StepIt pedal, and conduct the patient-reported outcome questionnaires at the various timepoints.

#### 5.5 **Outcome measures**

#### 5.5.1 **Primary outcome measures**

To assess the feasibility of conducting a full RCT in the future, the primary outcome measures are mainly:

#### Trial-related outcome measures

- Participants' compliance to StepIt exercise regime
- Recruitment and attrition rates, willingness of patients to be randomised, response rates to questionnaires, and degrees of missing data
- Testing of eligibility criteria and ability/willingness of clinical staff to partake in recruitment of participants

- Ability of site and clinicians to recruit and randomise patients, irrespective of care setting
- To assess any training requirements
- Adequacy of duration of follow-up (e.g. in relation to lymphoedema management and outcomes)
- Fitness for purpose of data collection methods including across and between care settings
- Adverse events

#### 5.5.2 Secondary outcome measures

The primary outcome for this pilot trial will be the feasibility of conducting a full RCT in the future. However, this study also aims to provide preliminary results regarding the acceptability and efficacy of a simple StepIt pedal as an adjuvant therapy for lymphoedema symptom control.

Clinical outcome measures

- Leg volume (see notes below), at week 0, 6, 12
  - Measured only between 9.30am to 3.30pm
  - Where possible the same rater is used for each participant; name of rater will be recorded.
- Ankle circumference measurement, using lateral malleolus as reference point (Brodovicz et al, 2009), at week 0, 6, 12
- Clinician's oedema severity score (Table 4 below; Nieman et al, 2013)

Table 4.	Clinician's	oedema	severity	/ score
TUDIC T,	chinciun 5	ocucina	JUVUII	, 20010

	0	1+	2+	3+	4+
Visible	No	yes	yes	yes	yes
Pitting	No	slight	>slight	>slight	'can't reach tibia'
Level	n/a	n/a	< knee	>knee	>knee

- Ankle range of motion (using goniometer)
- Pain score, at week 0, 6, 12
- Quality of life score, determined with EQ-5D-5L and LYMQOL-L Questionnaire, at week 0, 6, 12
- Participant opinion on trial participation, at week 12 (StepIt users only)
- Patient withdrawal rates due to change in management (e.g. need for surgery, hospital admission, infection, or other)
- Leg infection rates, primarily cellulitis

#### Leg volume measurement notes

The most optimal method for determining lymphoedema severity remains a bone of contention (Brodovicz et al, 2009; Hidding et al, 2016). However, leg volume measurement is considered an essential outcome to assess. Volumetric analysis using water displacement is considered the gold

standard direct method to measure limb volume, along with the more expensive perometry technique. However, due to potential issues arising when patients have a wound, eczema or cellulitis, water displacement measurements are less practical for legs compared to arms. Furthermore, in standard clinics, water displacement volumetry is a time-intensive method. The latest international consensus on management of lymphoedema recommends the measurement of leg volume using Kunhke's technique (Lee et al, 2015; Kunhke, 1978). Commencing at the ankle, with patient seated and leg elevated, the circumference is measured at 4 cm intervals, until seven measurements have been performed (total of 28 cm). The truncated cone formula is then used to calculate the volume for each segment, and the total, using:  $V = (1/3) * \pi * h * (r1^2 + r2^2 + (r1 * r2))$ 

Brijker and colleagues demonstrated that there is diurnal variation in leg volume (as measured by both water volumetric displacement and ankle circumference) and therefore the timing of performing the measurement. Volume can differ 5% depending on the time of day, with an increase observed particularly between 8am and 10am; a subsequent was observed at 5pm. During trial participation, therefore, patients need to attend for an appointment between 9.30am-3.30pm.

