#### 6. SUBJECTS

#### 6.1 Anticipated number of research subjects

This concerns a feasibility trial, and therefore the results from this study should inform a potential effect size for StepIt pedal exercise therapy, and also the degree in variance in lymphoedema volume changes (primary clinical outcome). To date, there is not sufficient published data to gain an insight in the effect that calf muscle exercise may have on lymphoedema symptoms. Guidance from a publication by Julious (2005) advises the use of 12 participants per treatment arm, and this approach will be taken here (see Table 5). Patient withdrawal rates before week 12 are not known at present and measuring this will be a primary aim

Table 5, sample size numbers required, based on hypothetical differences between published data and study outcomes

	Standard (control) arm	care	Standard care plus Steplt pedal arm
Patients (n)	12		12

Since this concerns a randomised controlled trial, albeit in the shape of a feasibility study, reprting will be done in line with CONSORT guidelines (Schulz, Altman & Moher 2010). The number of patients screened but who did not meet the inclusion criteria or who declined to participate will be recorded, as will any patients who are lost to follow-up (Appendix 2).

The patient attrition rate (withdrawal and loss to follow-up) will also be recorded, since this involves a study with at multiple visits, albeit incorporated into standard clinical appointments. Patients will be recruited from the adult (age 18+) population routinely seen by the evaluating clinical staff members.

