#### 8.2 **Primary outcome statistics**

The primary objective for this pilot study was the feasibility of conducting a larger scale randomised controlled trial. The secondary outcome statistics are other clinical and patient related outcomes measures.

The following descriptive statistics will be reported on:

- Number of patients screened
- Number of patients eligible/ineligible, and percentage of patients consented into the trial
- Number of patients completed the trial/discontinued (plus reasons if discontinued)

Lymphoedema control: Mann-Whitney U-test of change in leg volume (week 0 vs 12) between control and StepIt groups respectively.

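### Part of the protocol's own 5% diurnal difference in leg volume can enter the week 0 to 12 change, because the window opens before the stated morning rise ends and visit times are neither matched nor asked to be recorded

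*Protocol*

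**What the plan says.** The leg volume notes in Protocol 5.5.2 cite a study of diurnal variation: "Volume can differ 5% depending on the time of day, with an increase observed particularly between 8am and 10am". The rule is presented as following from this: "During trial participation, therefore, patients need to attend for an appointment between 9.30am-3.30pm". The list of clinical outcomes in the same section repeats the window: "Measured only between 9.30am to 3.30pm".

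The list also standardises one condition within the participant: "Where possible the same rater is used for each participant; name of rater will be recorded". No matching rule is given for the time of day, and no section asks for the clock time of the measurement.

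The measurement is used as a change score. Section 8.2 specifies a "Mann-Whitney U-test of change in leg volume (week 0 vs 12) between control and StepIt groups respectively". Section 6.1 says the results should inform a potential effect size and "also the degree in variance in lymphoedema volume changes (primary clinical outcome").

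**The concern.** A window common to all participants limits how far they differ from one another. A change score needs something else: that the same person is measured under similar conditions at both visits. Here the two visits of one person may lie up to six hours apart on the clock, and one of them may fall within the period when, by the protocol's own account, volume is still rising.

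At stake is the precision of the clinical outcome that a later full trial would be sized on. Time-of-day differences between a participant's own visits add to the variance of change and have nothing to do with the pedal or the disease. If the clock time is not recorded, no later analysis can separate them out.

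**Working it through.** **Inputs from the protocol.** Diurnal difference 5%, for the day as a whole; rise particularly 8am to 10am; window 9.30am to 3.30pm (6 hours); 12 participants per arm. The 5% is a literature value and the 12 per arm is a rule of thumb ("advises the use of 12 participants per treatment arm, and this approach will be taken here"), with no alpha, power, effect or SD behind it. There is therefore no plan figure to reproduce.

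**Overlap.** 10.00 − 9.30 = 0.5 h. That is 0.5/2 = 25% of the rise period and 0.5/6 = 8.3% of the window. With uniform booking, the chance that at least one of a participant's week 0 and week 12 visits falls before 10am is 1 − (11/12)² = 16%.

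**Assumptions.** The protocol does not say how much of the 5% falls inside the window, so four profiles are assumed, each totalling 5% and made of straight-line pieces. Visit times at weeks 0 and 12 are taken as independent and uniform over the window. Results are in percentage points of leg volume. The SDs come from 400,000 simulated visit pairs.

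| Assumed profile | Largest shift in window | Added SD of change | Largest shift, 10.00 start only | SD (largest shift), 10.00 start and within 1 h of week 0 |
|---|---|---|---|---|
| (a) All 5% in 8–10am, then flat | 1.25 | 0.29 | 0.00 | 0.00 (0.00) |
| (b) Half in 8–10am, half by 5pm | 2.59 | 0.92 | 1.96 | 0.20 (0.36) |
| (c) Half in 8–10am, half by 3.30pm | 3.12 | 1.16 | 2.50 | 0.25 (0.45) |
| (d) Linear 8am to 5pm | 3.33 | 1.36 | 3.06 | 0.31 (0.56) |

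Hand checks:
- (a) The slope is 5/2 = 2.5 points per hour, and 2.5 × 0.5 = 1.25.
- (b) 1.25 × 0.5 + (2.5/7) × 5.5 = 0.625 + 1.964 = 2.59.
- (d) The slope is 5/9 = 0.556 points per hour, and 0.556 × 6 = 3.33. The difference of two independent uniform times on 6 h has SD 6/√6 = 2.45 h, and 2.45 × 0.556 = 1.36.

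**Effect on the variance.** Inflation is (added SD / true SD)². The documents give no true SD of change; 3 to 5 points is assumed. Lowest: (0.29/5)² = 0.3%. Highest: (1.36/3)² = 21%.

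**Effect on this trial's contrast.** The chance difference between arms due to timing alone has standard error SD × √(2/12): 0.29 × 0.408 = 0.12 and 1.36 × 0.408 = 0.56 points.

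**Effect on a later trial (illustration).** Assume a 3-point difference, two-sided 5% and 80% power. An added SD of 1.0 on a true SD of 3, 5 or 8 points raises n per arm from 16 to 18, 44 to 46 and 112 to 114.

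**Which part of the remedy does the work.** Moving the start to 10.00am alone still leaves a shift of 0 to 3.06 points. Unless the whole 5% occurs before 10am, matching the time within the participant matters more than the later start.

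**The case against.** A reader might infer that the full 5% can enter the change score. The text does not support that. The 5% describes the whole day, and the window already leaves out 8.00 to 9.30am, three quarters of the stated rise period, as well as 5pm. If the 5% were spread linearly over 9.30am to 3.30pm, the added SD would be 5/√6 = 2.04 points and the variance inflation (2.04/5)² to (2.04/3)², or 17% to 46%. That profile fits poorly with a rise placed mainly at 8 to 10am.

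A reader might also infer that timing could pass for a pedal effect. Under randomisation it is ordinary random error, which the between-group comparison already reflects. The protocol describes no mechanism by which times would differ by arm, although unblinded scheduling does not rule it out.

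Other points carry some weight:
- Leg volume is a secondary outcome in a feasibility study. A variance obtained under routine booking is relevant if the full trial books in the same way.
- Uniform, independent booking is assumed. If participants tend to keep similar slots, the effect shrinks.
- Visits sit within routine appointments. A rigid time band could compete with same-rater booking and cost visits, while attrition and missing data are primary outcomes.
- The case report form is not shown and may carry a time field.
- The rationale sentence is incomplete ("a subsequent was observed at 5pm"), and it does not say that the window was meant to exclude the whole rise. Nothing here rests on the missing word.

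These points limit the size and argue for a flexible rule. They do not remove the mismatch between the stated reason and the window, or the absence of any within-person time rule.

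**Conclusion.** The point holds in limited form. The window starts before the rise that the protocol gives as its reason has ended, and the protocol neither matches each participant's time of day across visits nor asks for it to be recorded. Part of the 5% can therefore enter the week 0 to 12 change: at most about 1.25 to 3.33 points for one participant, with an added SD of about 0.29 to 1.36 points. These figures depend on the assumed profiles and booking pattern, and the 0.3% to 21% variance inflation also depends on the assumed true SD. The effect is small to moderate, and mainly noise. It is worth correcting because the variance of this change is a stated output and the correction is cheap.

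**What to change.** Change both places in 5.5.2 where the window is stated:
- Open the window at 10.00am.
- Where possible, book each participant's week 6 and week 12 measurements within about 1 hour of the clock time of their week 0 measurement, worded like the existing same-rater rule.
- Record the clock time at every measurement, without exception, so that mismatched visits can be flagged or examined in a sensitivity analysis.
- State that a visit outside the band is still measured and flagged, not missed.

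The cost is a sentence or two in the protocol and one time field, if the case report form does not already have it. Booking within routine appointments becomes slightly less flexible, which the existing allowance of two weeks either side of weeks 6 and 12 helps to absorb. No extra visits are needed.

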#### 6. SUBJECTS

#### 6.1 Anticipated number of research subjects

This concerns a feasibility trial, and therefore the results from this study should inform a potential effect size for StepIt pedal exercise therapy, and also the degree in variance in lymphoedema volume changes (primary clinical outcome). To date, there is not sufficient published data to gain an insight in the effect that calf muscle exercise may have on lymphoedema symptoms. Guidance from a publication by Julious (2005) advises the use of 12 participants per treatment arm, and this approach will be taken here (see Table 5). Patient withdrawal rates before week 12 are not known at present and measuring this will be a primary aim

Table 5, sample size numbers required, based on hypothetical differences between published data and study outcomes

	Standard (control) arm	care	Standard care plus Steplt pedal arm
Patients (n)	12		12

Since this concerns a randomised controlled trial, albeit in the shape of a feasibility study, reprting will be done in line with CONSORT guidelines (Schulz, Altman & Moher 2010). The number of patients screened but who did not meet the inclusion criteria or who declined to participate will be recorded, as will any patients who are lost to follow-up (Appendix 2).

The patient attrition rate (withdrawal and loss to follow-up) will also be recorded, since this involves a study with at multiple visits, albeit incorporated into standard clinical appointments. Patients will be recruited from the adult (age 18+) population routinely seen by the evaluating clinical staff members.

#### 6.1.1 Randomisation

A 1:1 allocation to the control and intervention group respectively will be applied. Following written consent patients will be allocated at random to the control or intervention group, using a non-restricted randomised sequence generated for the whole sample using a free ware randomisation programme, see https://www.randomizer.org/. Sequential envelopes with each next randomisation allocation will be used to achieve concealment.

The researcher/lymphoedema care specialist will inform the patient what arm they have been allocated. As the study involves the Clinical Lymphoedema Specialist or Researcher consenting and following up patients and a self-administered intervention of necessity it is not possible to achieve blinding for the participants or the Clinical Lymphoedema Specialists.

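### Allocation is not held until the week-0 measures are done, so in this unblinded trial the baseline can be recorded with the arm already known

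*Protocol*

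**What the plan says.** **Trigger for allocation (6.1.1).** "Following written consent patients will be allocated at random to the control or intervention group". Sequential envelopes are used for concealment, and no other precondition is given.

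**Knowledge of the arm (6.1.1).** "The researcher/lymphoedema care specialist will inform the patient what arm they have been allocated", and "it is not possible to achieve blinding for the participants or the Clinical Lymphoedema Specialists".

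**Who does what (5.4).** The Clinical Lymphoedema Specialist measures leg volume. The specialist or a researcher "will randomise the patient, hand out the StepIt pedal, and conduct the patient-reported outcome questionnaires at the various timepoints".

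**Baseline (5.3).** After describing randomisation, pedal issue and the end-of-trial questions, the section says: "All participants will have demographic data obtained and the following base line measures (Table 3". Table 3 places leg volume, ankle circumference, ankle range of motion, pain score, LYMQOL-Leg and EQ-5D-5L at week 0.

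**Use of week 0 in the analysis.** Section 8.2 plans a "Mann-Whitney U-test of change in leg volume (week 0 vs 12) between control and StepIt groups respectively". Section 8.3 compares the arms on the difference in ankle range of motion between first and last visit. It compares quality of life by Mann-Whitney test at the visits, does not say whether ankle circumference is compared as a change, and names no test for pain.

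**The concern.** A baseline is protected from the allocation only if it is recorded before anyone involved knows the arm. Here the patient who scores pain and quality of life knows the arm once told, and so does the specialist who tapes the leg. If the envelope is opened straight after consent, the week-0 values become post-randomisation values that serve as the baseline.

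The protocol accepts that blinding of patients and specialists cannot be had, so some exposure at weeks 6 and 12 is built in. Week 0 is different, because the order of events alone can protect it.

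The estimate also has a further use. Section 6.1 says the results should inform a possible effect size and the variance of volume change. A distorted baseline would carry into the planning of a later trial.

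**Working it through.** No figure in the protocol is in dispute. The sample size ("advises the use of 12 participants per treatment arm, and this approach will be taken here") is a rule of thumb with no calculation behind it to reproduce. The check is a reading of the text, followed by a short account of how a week-0 shift would act.

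**1. What the text says about order**

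| Section | Content | Order of week-0 measures and allocation |
|---|---|---|
| 6.1.1 | Consent, then allocation | Week-0 measures not mentioned |
| 5.3 | Randomisation and pedal, then end-of-trial questions, then baseline measures | Baseline comes last in the text, but the paragraph is not chronological |
| 5.4 | Leg volume by the specialist; next sentence: randomise, pedal, questionnaires | Questionnaires named after randomisation, leg volume before it; may be a task list |
| 6.3 | Follow-up dates counted from the baseline visit | None stated |
| Appendix 2 | Participant flowchart | Not seen |

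No readable text places the week-0 measures before allocation as a requirement, and none states that they come after it. A site could open the envelope directly after consent and still comply with 6.1.1.

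**2. How a shift would act**

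Let *e0* and *e12* be the arm-related differences (StepIt minus control) in recorded values at weeks 0 and 12 that arise from knowing the arm. Then

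expected between-arm difference in change = true effect + *e12* − *e0*.

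- If the shift occurs at week 0 only (*e12* = 0), all of *e0* enters the result. A StepIt leg read too large at week 0 looks as if it shrank.
- If the same shift recurs at week 12 (*e12* = *e0*), it cancels.
- Adjusting week 12 for week 0 with slope *b* leaves −*b* × *e0*, so adjustment does not remove the shift unless *b* is zero.

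**3. Scale in millilitres (illustration only)**

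Assume circumferences rising evenly from 26 to 44 cm. With r = C/2π, the truncated-cone formula in 5.5.2 gives V = L/(12π) × (C1² + C1·C2 + C2²).

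- Over 28 cm: 28/37.70 × (676 + 1,144 + 1,936) = 28/37.70 × 3,756 ≈ 2,790 mL.
- With 0.5 cm added at every level (26.5 to 44.5 cm): 28/37.70 × 3,861.75 ≈ 2,868 mL, which is 78.5 mL or 2.8% more.
- Seven circumferences at 4 cm spacing span six segments, or 24 cm. On that reading the volume is about 2,391 mL and the shift about 67 mL, again 2.8%.

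The circumferences and the 0.5 cm are assumptions. The protocol gives no figure for either.

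**4. Effect on the test (illustration only)**

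Inputs: 12 per arm (6.1), Mann-Whitney test (8.2), and assumed normal changes with SD 1, no true effect and a two-sided 5% level (the protocol states no level). From 20,000 simulated trials per row:

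| Week-0 shift (SD of change) | Rejection rate |
|---|---|
| 0 | 4.4% |
| 0.1 | 5.1% |
| 0.25 | 8.3% |
| 0.5 | 19% |
| 1.0 | 61% |

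With no standard deviation in the protocol, the millilitre figures cannot be mapped onto these rows. The table shows sensitivity and does not predict the bias in this trial.

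**The case against.** The strongest reply is that the protocol never says allocation comes first. Consent as a precondition leaves room for the baseline measures between consent and the envelope. Section 5.3 is no guide to sequence, since it mentions the discharge visit before the baseline. Section 5.4 assigns tasks, and it mentions leg volume before randomisation. The order may be drawn in the Appendix 2 flowchart, whose absence from the copy reviewed is no fault of the plan. All of this stands. A reader might infer that the protocol places allocation before the week-0 measures, but the text does not support that. It supports only that the order is not fixed.

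Three other stronger readings also fail:

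- **That every change from baseline is biased.** Only leg volume and ankle range of motion are explicitly analysed as change. Bias also needs both the unfavourable order and an arm-related shift, and neither is shown. A taping habit that persists to week 12 largely cancels, and 5.5.2 asks for the same rater where possible.
- **That patients who leave on hearing their allocation are lost because they lack a baseline.** Under 6.3 no further data are collected after withdrawal, so such a patient has no week-12 value and leaves the change analysis whichever order is used.
- **That the false-positive rate is raised by a known amount.** The rates above follow from assumed shifts alone.

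It is also fair to say that feasibility is the primary objective and that efficacy results are preliminary, which limits the consequence. It does not remove the point: the volume change is still tested and is still meant to inform a later trial.

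**Conclusion.** The point holds in a limited form. Consent is the only stated precondition for allocation, patients and specialists are unblinded, and no readable text holds the envelope until the week-0 measures are done. This leaves week-0 leg volume, ankle measures, pain and quality-of-life scores open to knowledge of the arm. It also leaves the two stated change analyses open to bias.

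The size of any bias is unknown and may be nil. It depends on the order sites actually use and on a shift at week 0 that is not repeated at week 12. If the unseen flowchart already puts baseline first, what remains is to make 6.1.1 say so.

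The change is still worth making. The order of baseline and allocation is a matter of trial conduct, and no analysis can restore a baseline recorded after the arm was known.

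**What to change.** In 6.1.1, state that the next allocation envelope is opened only after written consent and after all week-0 measures in Table 3 have been completed and dated: leg volume, ankle circumference, ankle range of motion, pain score, LYMQOL-Leg and EQ-5D-5L. Reorder 5.3 and the task sentence in 5.4 to match (baseline measures and questionnaires, then randomisation, then pedal issue). Check the Appendix 2 flowchart and align it if needed.

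The cost is protocol wording and a reordered visit checklist, with no extra visit, staff or measurement. The small downside is that patients learn their allocation at the end of the visit. The sample size is unaffected. The change does nothing about unblinded assessment at weeks 6 and 12, which remains a separate limitation.
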